### **New lesions**

Lesions will be considered new if they were not present at the baseline timepoint, but are visible at the current timepoint.

A node consistent with lymphoma will be recorded as a new lesion if it was previously normal in size and is now  $>1.5$  cm in LDi. An unequivocal, new extranodal lesion consistent with lymphoma of any size is considered a new lesion. If multiple new extranodal lesions are noted, at least one should be recorded as a new lesion.

New lesions must be consistent with lymphoma rather than another etiology (eg, infection, inflammation) and must be PET-positive, if PET is available. New lesions will be treated as PET-positive when PET is not available to confirm avidity.

Some types of truly non-measurable lesions generally require further verification that they are attributable to lymphoma through biopsy or cytology. These include ascites, pleural or pericardial effusions, and lytic bone lesions. They may be recorded as new lesions only when there is other evidence of progression.

Other truly non-measurable lesions will not require verification to be considered a new lesion, as long as their appearance is unequivocal in the judgment of the reviewer:

- Non-measurable lesions such as brain and CNS lesions including leptomeningeal disease attributable to lymphoma
- Non-measurable nodal masses such as infiltrative mesenteric masses or retroperitoneal masses

Extranodal lesions which disappeared and then reappeared at a later timepoint will be considered indicators of progression.

### **Spleen response**

The spleen will be measured in the craniocaudal length as at baseline, and the enlarged portion calculated by subtracting 13 cm. Response categories for the spleen are as defined below:

- Normal (CR): Spleen was enlarged at baseline and has regressed to  $\leq 13$  cm at the current timepoint or the spleen was assessed as normal at baseline and is still normal, or there is radiological evidence of splenectomy at baseline.
- Partial Resolution (PR): Spleen was assessed as enlarged at baseline, and its excess length has decreased by  $\geq 50\%$ .
- Stable Splenomegaly (SD): No decrease consistent with PR and no increase consistent with progression

- Unequivocal increase (PD): The spleen is assessed as PD if any of the following are true:
  - Recurrent splenomegaly: A spleen which was abnormal at baseline (>13 cm) first returned to normal, but at the current timepoint the spleen increases by >2 cm from its nadir and the length is >13 cm.
  - New splenomegaly: No prior splenomegaly and spleen increases by >2 cm from baseline and the length is >13 cm.
  - Progression of existing splenomegaly: A spleen which is abnormal at baseline has the enlarged portion increase by  $\geq 50\%$ , and by  $\geq 1$  cm in absolute measurement, at the current timepoint from its nadir value.

### **Liver response**

The liver will be assessed qualitatively. Response categories are as defined below:

- Non-pathological: Liver was assessed as enlarged at baseline and has regressed to a normal size, or still enlarged but without evidence of lymphoma involvement, OR the liver was assessed as normal at baseline and continues to be normal.
- Enlargement: Liver is considered stable if there is persistent liver involvement with evidence based on imaging (CT or MRI) or biopsy that there is infiltration by lymphoma of the entire organ.

### **Anatomic Response**

The anatomic response should be assessed at each post-baseline timepoint based on the criteria below. Liver size alone should never be the basis for response determination by itself, but only support the assessment as supplemental information.

Target	Non-Target	Spleen	New Lesions	Anatomic Response
CR	CR	CR	No	CR a
CR	CR	PR	No	PR b
CR	SD	CR	No	PR b
PR	CR/SD	CR/PR	No	PR
PR	CR/SD	SD	No	SD
SD	CR/SD	CR/PR	No	SD
SD	CR/SD	CR/PR/SD	No	SD
Any non-PD	NE	CR/PR/SD	No	NE
NE	Any non-PD	CR/PR/SD	No	NE
PD	Any	Any	Any	PD
Any	PD	Any	Any	PD
Any	Any	PD	Any	PD
Any	Any	Any	Yes	PD
Abbreviations: CR=complete response; NE=not evaluable; PD=progressive disease; PR=partial response; SD=stable disease. a If the liver shows lymphoma involvement, it must resolve to allow CR. b Spleen can drive PR on its own if no target lesions were identified at baseline.				

#### 10.9.2.4 Metabolic Response

In addition to anatomic imaging, metabolic imaging using FDG-PET can contribute to the assessment, if it is available, or may form the sole basis for response if no anatomic imaging is performed at a time point. An FDG-PET is required at screening. Subsequent time points that require PET are shown in the schedule of assessments. If lesions are not FDG-avid at baseline, PET is not required at follow-up timepoints unless clinically indicated.

##### PET Assessment

For every FDG-PET scan, a SPS score is obtained by comparing the maximum standard uptake value of the lesion that shows the greatest tracer uptake (the “hottest” lesion) to surrounding normal tissue, to a ROI placed over blood in the heart or major vessels of the mediastinum (the “mediastinal blood pool”) and to an ROI placed over normal liver.

Depending on the uptake, a score between 1 and 5 will be assigned as follows:

Score	Definition
1	No uptake above background
2	Uptake above background, but below mediastinal blood pool
3	Uptake >mediastinal blood pool, but ≤uptake in liver
4	Uptake moderately higher than liver
5	Uptake markedly higher than liver (maximum standard uptake value >2 × normal liver) OR (after treatment has started) New FDG-positive lymphoma lesions

After screening, in addition to the 5-point scale score the assessment of the FDG-PET also involves an assessment of the overall uptake (a combination of extent and intensity) by tissue consistent with lymphoma, and comparison of this uptake to the baseline and to the scan on which the overall uptake was lowest (nadir).

#### Metabolic response determination

Metabolic response categories are defined as follows:

Metabolic Response	Definition
Complete metabolic response (CMR)	A score of 1, 2, or 3.
Partial metabolic response (PMR)	A score of 4 or 5 (without new lesions), AND Overall uptake decreased compared with baseline
Stable metabolic disease (SMD)	A score of 4 or 5 (without new lesions), AND Overall uptake unchanged compared with baseline and nadir
Progressive metabolic disease (PMD)	A score of 4 or 5 with overall uptake increased compared with nadir, OR with new FDG-positive lesions consistent with lymphoma

In Waldeyer's ring or extranodal sites with high physiologic uptake or with activation within spleen or marrow (eg, with chemotherapy or myeloid colony-stimulating factors), uptake may be greater than normal mediastinum and/or liver. In this circumstance, CMR may be inferred if uptake at sites of initial involvement is no greater than surrounding normal tissue, even if the tissue has high physiologic uptake.

#### Clinical Data

##### Bone marrow assessment

To allow an overall response of CR, the bone marrow must be clear of lymphoma (negative for lymphoma).

Lugano allows assessment of bone marrow based on FDG-PET if the lymphoma type is FDG-avid. Bone marrow on FDG-PET may be normal, may show diffuse uptake (clinical judgment is required, because this is also compatible with reactive changes due to chemotherapy or colony-stimulating factors), or may show focal increased uptake that is strongly indicative of lymphoma.

Note: In this protocol, if there is bone marrow involvement, bone marrow is required to confirm CR, regardless of FDG-avidity.

A negative PET allows the bone marrow to be declared negative, even without biopsy, and would support a CR overall (diffuse uptake compatible with reactive changes from chemotherapy or growth factor use can fall into this category). A PR may occur with residual uptake higher than uptake in normal marrow but reduced compared with baseline. If there are persistent focal changes in the marrow in the context of a nodal response, consideration should be given to further evaluation with MRI or biopsy or an interval scan.

Bone marrow aspirate or biopsy is required only as clinically indicated, or if FDG-PET evaluation of bone marrow is judged inconclusive. For lymphoma that is shown at baseline to be non FDG-avid, both aspiration and biopsy are required to declare marrow to be negative. If bone marrow biopsy is performed and shows lymphoma, the bone marrow is considered positive, regardless of the results of the PET.

#### *Physical examination findings*

On rare occasions, lesions may be present on physical examination that are not seen on imaging at all. An example might be lymphadenopathy in the popliteal fossa, when the “whole body” imaging includes only anatomy to the mid femur. Such lesions should be documented as non-target lesions in study forms. They can contribute to progression if new lesions appear this way, and if any were present at baseline, they must disappear for an overall response of CR.

#### *Other clinical data*

Information on the use of hematopoietic growth factors and other medications can affect the response assessment as described above.

At certain protocol-specified time points, additional tissue biopsies may be collected and incorporated into the response assessment.

### **10.9.2.5 Overall Response**

Overall response at each timepoint is determined by combining the anatomic response, metabolic response, and clinical data. When both CT and FDG-PET are available, the overall response is driven primarily by the metabolic response. When only one imaging modality is available at a given timepoint, that modality is the main determinant of overall response.

Metabolic Response	Anatomic Response	Bone Marrow	Physical Examination	Overall Response
CMR	CR, PR, or SD	Negative	No lesions	CR
PMR	CR, PR, or SD	Any	No new lesions	PR
SMD	CR, PR, or SD	Any	No new lesions	SD
PMD	Any	Any	Any	PD
Any	PD	Any	Any	PD
Abbreviations: CMR=complete metabolic response; CR=complete response; PD=progressive disease; PMD=progressive metabolic disease; PMR=partial metabolic response; PR=partial response; SD=stable disease; SMD=stable metabolic disease.				

During determination of overall response, if no FDG-PET was performed at the timepoint in question, the results of a preceding PET may be “carried forward”, unless there has been worsening of disease on the CT. For example, if a post-baseline assessment shows a CMR on the PET, and PR on the CT, the overall response is CR. If the next timepoint shows continued PR on the CT, but there is no PET available, the overall response for that visit is still CR.

Lugano Classification 2014 [Cheson, B. D., et al 2014]

Barrington, SF et al 2014 [Barrington, S. F., et al 2014]

### 10.9.3 Application of the IWWM Classification for Treatment Response Assessment

IWWM Criteria 2014 are provided in [Dimopoulos, M. A., et al 2014].

#### 10.9.3.1 Overview

This appendix describes the process for assessing treatment response according to the IWWM Criteria for WM [Dimopoulos, M. A., et al 2014]. Assessments include:

- Imaging of abnormal lymph nodes
- Imaging of spleen and liver
- Measurements of serum IgM
- Detection of IgM by immunofixation
- Measurements of cryoglobulins
- Bone marrow biopsy
- Constitutional symptoms

- Plasmapheresis
- Amyloid (if applicable)

At baseline/screening, the participant should be assessed for the presence of extramedullary disease. If extramedullary disease is present, imaging should be used to assess the disease at baseline and follow-up timepoints. If there is no extramedullary disease at screening/baseline, then imaging does not need to be repeated at subsequent follow-up timepoints, unless clinically indicated.

Anatomic imaging may include CT, MRI or some combination of the 2. CT is the most common modality used, and for the purposes of this document the term “CT” will be used to represent all anatomic imaging, no matter which imaging modality is used.

Before treatment (“baseline”), if extramedullary disease is present on CT, all malignant lymph nodes (“nodal lesions”) will be classified as “target” (selected for quantitative assessment) or as “non-target” (selected for qualitative assessment). All focal non-nodal lesions are followed as non-target. The spleen will be assessed quantitatively (by measuring the craniocaudal length). If biopsy is performed, or if there are any physical examination findings that cannot be evaluated by imaging, these should be documented.

After therapy has begun, target lesions, non-target lesions, and the presence of new lesions in images will be assessed to provide a collective response in focal lesions (usually referred to as the “lymph node response” because the great majority of the focal lesions are lymph nodes). The spleen size will be assessed separately from focal lesions for an organomegaly response. Imaging responses (when applicable) are combined with changes in the clinical data (including serum IgM, immunofixation, cryoglobulinemia, bone marrow, constitutional symptoms, plasmapheresis, and amyloidosis) to produce an overall response at each timepoint.

### **10.9.3.2 Anatomic Disease Assessment**

Anatomic assessment specifically refers to the size of focal lesions or organs, assessed using computed tomography or magnetic resonance imaging. As stated previously, for simplicity the term “CT” will be used to represent all anatomic imaging.

#### **10.9.3.2.1 Screening (Baseline) Assessment**

##### **Documentation of focal lesions**

If extramedullary disease is present, all focal lesions are identified at screening and classified as measurable or non-measurable. Up to 6 lesions are selected as “target” lesions, which are then followed quantitatively throughout the study. All other focal lesions are documented as “non-target” lesions and evaluated qualitatively thereafter.

### **Measurable and non-measurable lesions**

Malignant lymph nodes (nodal lesions) are considered measurable if they are considered to be due to WM/LPL, are clearly and reproducibly measurable in 2 dimensions in the axial plane, and measure >1.5 cm in LDi when assessed by CT/MRI scan, irrespective of scanner type and slice thickness/interval.

Lesions considered non-measurable include:

- Uni-dimensionally measurable lesions (clearly measurable in only one dimension)
- Extranodal lesions which are considered to be clearly due to WM/LPL

### **Target and Non-target Lesions**

Up to 6 target lesions will be selected from among the measurable lesions and documented as target lesions. Target lesions should be selected based on their size (largest lesions preferred) and suitability for reproducible measurements. Measurements of the LDi and longest perpendicular, or “SD1” should be made in the axial plane on the slice of the lesion with the longest in-plane diameter. Calculate the product of PPD for each target lesion and the SPD for all target lesions.

Non-target lesions will be all focal (nodal or extranodal) lesions not chosen as target lesions, whether they were measurable or not.

Once lesions are designated as target or non-target, those designations may not change during later assessments.

### **Spleen Assessment at Baseline**

Splenic disease will be assessed quantitatively, independent of the assessment of measurable and non-measurable focal lesions. The spleen will be measured in the cranial to caudal axis, and all spleen measurements referred to hereafter will refer to this craniocaudal length. The spleen is considered normal if the length is less than 13 cm (or if the spleen has been removed surgically). It is considered enlarged if it is greater than or equal to 13 cm in length. The portion of the measurement that exceeds 12.9 cm will be referred to as the abnormal portion, or the excess length.

#### **10.9.3.2.2 Post-baseline Assessment**

##### **Target lesions**

At each follow up visit, target, non-target lesions and the presence of new lesions in images will be assessed to provide a collective lymph node response.

- Complete Response (CR): All target lymph nodes must have regressed to normal size defined as  $\leq 1.5$  cm in LDi. Target extranodal sites must be absent (0 by 0 cm).

- Partial Response (PR):  $\geq 1\%$  decrease in SPD of target lesions from baseline, and no individual lesion meets the criteria for progression.
- Progressive Disease (PD): Target lesion progression is based on either a  $\geq 50\%$  increase in the SPD of all target lesions, or a  $\geq 50\%$  increase in the LDi of any single target lesion from its nadir (smallest size previously seen, which can include the baseline if that is the smallest), which meets all of the following requirements
  - The final size of the individual lesion must be  $> 1.5$  cm in LDi
  - And one of the following:
    - For lesions  $< 2$  cm at nadir, the lesion's LDi must have increased by  $\geq 0.5$  cm at the current timepoint from its nadir.
    - For lesions  $\geq 2$  cm at nadir, the lesion's LDi must have increased by  $\geq 1$  cm at the current timepoint from its nadir.
- Stable Disease (SD): A target lesion assessment of SD requires all of the following:
  - Target lesions do not meet the criteria for CR or PR
  - No individual lesion meets the criteria for progression
- Not Evaluable (NE): When any target lesion identified at baseline cannot be evaluated at a post-baseline timepoint due to missing imaging, poor image quality, changes in the lesion or background that precludes assessment, or focal therapy or other procedures that change the lesion size, the target lesion assessment will be NE, unless progression is identified in another target lesion.

### **Non-target lesions**

Non-target lesions will be assessed at each post-baseline timepoint individually and as a group. Response categories are as defined below:

- Absent/Normalized (CR): All individual non-target nodal lesions must have returned to normal size. All extranodal lesions must have disappeared.
- Unequivocal Progression (PD): Any individual non-target lesion must unequivocally progress in the context of the overall disease burden to be assessed as PD. For increased thickening of the wall of a hollow viscus, the reviewer will use their cautious judgment to determine whether the increase is most likely caused by disease progression.

- PD should not be called based solely on enlarging pleural effusions or ascites or enlarging lytic bone lesions. Rather, the overall assessment should be based on the rest of the disease burden.
- Stable Disease (SD): At least 1 non-target lesion is still present, or a lymph node enlarged, without any individual lesions showing unequivocal progression.
- Not Evaluable (NE): When an individual non-target lymph node, extranodal lesion, or non-measurable disease manifestation cannot be assessed at a post-baseline timepoint due to missing imaging, poor image quality, changes in the lesion or background that precludes assessment, or focal therapy to a lesion, the individual non-target lesion will be assessed as NE. The assessment of the non-target lesions as a whole will be NE if any of the non-target lesions are NE and none are PD.

### **New lesions**

Lesions will be considered new if they were not present at the baseline timepoint but are visible at the current timepoint.

A node will be recorded as a new lesion if it was previously normal in size and is now >1.5 cm in LDi, and the change in size and the node morphology indicate malignancy. An unequivocal, new extranodal lesion of any size is considered a new lesion. If multiple new lesions are noted, at least one should be documented individually as a new lesion.

New lesions must be strongly believed to be due to WM/LPL rather than another etiology (eg, infection, inflammation).

Some types of truly non-measurable lesions generally require further verification that they are attributable to WM/LPL through biopsy or cytology. These include ascites, pleural or pericardial effusions, and lytic bone lesions. They should be recorded as new lesions only when there is other evidence of progression.

Other truly non-measurable lesions will not require verification to be considered a new lesion, as long as their appearance is unequivocal in the judgment of the reviewer:

- Non-measurable lesions in the central nervous system, attributable to WM/LPL
- Non-measurable nodal masses such as infiltrative mesenteric or retroperitoneal masses

Extranodal lesions which disappeared and then reappeared at a later timepoint will cause a determination of progression, just like a new lesion, but are not designated “new”.

### **Spleen response**

The spleen will be measured in the craniocaudal length as at baseline, and the enlarged portion calculated by subtracting 12.9 cm. Response categories for the spleen are as defined below:

- Normal (CR): Spleen was enlarged at baseline and has regressed to  $<13$  cm at the current timepoint, or the spleen was assessed as normal at baseline and is still normal, or there is radiological evidence of splenectomy at baseline, or the spleen was normal at baseline, and there has been a splenectomy since then.
- Partial Response (PR): Spleen was assessed as enlarged at baseline, and its excess length has decreased by  $\geq 1\%$ .
- Stable Disease (SD): No decrease consistent with PR and no increase consistent with progression.
- Progressive Disease (PD): The spleen is assessed as showing PD if any of the following are true:
  - Recurrent splenomegaly: A spleen which was abnormal at baseline ( $\geq 13$  cm) first returned to normal, but at the current timepoint the spleen has significantly increased as judged by reviewer(s) and the length is  $\geq 13$  cm.
  - New splenomegaly: No prior splenomegaly. The spleen has increased significantly as judged by reviewer(s) from baseline and the length is  $\geq 13$  cm.
  - Progression of existing splenomegaly: A spleen which was abnormal at baseline has the significantly enlarged as judged by reviewer(s)

The combined radiology response will be determined as follows:

### **Radiology Response**

Target	Non-target	New lesions	Spleen Response	Radiology Response
CR	CR	No	CR	CR
CR	SD	No	PR/CR	PR
PR	CR/SD	No	PR/CR	PR
PR	CR/SD	No	SD	SD
SD	CR/SD	No	Any but PD	SD
Any non-PD	NE	No	Any but PD	NE
NE	Any non-PD	No	Any but PD	NE
Any non -PD	Any non-PD	No	NE	NE
PD	Any	Yes/No	Any	PD
Any	PD	Yes/No	Any	PD
Any	Any	Yes	Any	PD
Any	Any	Yes/No	PD	PD
NA	NA	No	Normal (CR)	NED
Abbreviations: CR=complete response; NA=not applicable; NE=not evaluable; NED=no evidence of disease; PD=progressive disease; PR=partial response; SD=stable disease. NA – No lesions of this type present at baseline. NED – No lesions of any kind seen at baseline, and none present at visit being evaluated.				

### **Clinical data**

At each follow-up timepoint, serum IgM measurements, detection of IgM by immunofixation, cryoglobulin measurements, physical exams, bone marrow biopsy assessments, constitutional symptoms, plasmapheresis, and amyloid (if applicable) are assessed and will also be considered as part of the response assessment.

### 10.9.3.3 Overall Response

Overall response for each timepoint is defined below.

#### Response category definitions

#### Overall Timepoint Assessment

Response and Sub-categories for assessment	Overall Timepoint Assessment
Complete Response (CR)	Complete resolution of disease (all of the following)
Serum IgM	CR (Normal Serum IgM from baseline)
Serum M-Protein Immunofixation	Negative If immunofixation status is not reported/not interpretable for any available timepoints, the best possible response is VGPR. One negative immunofixation is sufficient to be called CR for a particular visit. Once a negative immunofixation has been reported for a visit, any subsequent visits with immunofixation status not reported or not interpretable can be CR as long as all remaining data supports a continued CR status.
Extramedullary Disease by Physical Examination	No EMD Present
Cryoglobulinemia	
 
Negative cryoglobulinemia if cryoglobulinemia was Positive at baseline.
 
If cryoglobulinemia was negative or not available at baseline, a negative cryoglobulinemia assessment at post-baseline is not required for an overall timepoint assessment of CR.
 

Radiology Overall Response	CR or NED
Bone Marrow	Negative Negative assessment of bone marrow is required to confirm CR even if bone marrow is negative at baseline. Once a CR has been confirmed by bone marrow then repeat bone marrow is not required.
Other Confounding Factors	No If amyloidosis was present at baseline, then it must be absent. No new symptomatic disease should be observed.
Very Good Partial Response	At least one sub-category does not meet the criteria for CR; none of the sub-categories meet the criteria for PD; and responses are described below:
Serum IgM	VGPR or CR ( $\geq 90\%$ reduction in Serum IgM or normal from baseline)
Radiology Overall Response	CR or PR
Extramedullary Disease by Physical Examination	
 
Spleen and/or Lymph nodes which were assessed as Enlarged at baseline are assessed as Normal/Not Enlarged or
 
No EMD is present at baseline and post-baseline
 

New Symptomatic Disease	Absent

Response and Sub-categories for assessment	Overall Timepoint Assessment
Partial Response	All criteria have to met
Serum IgM	PR ( $\geq 50\%$ and $< 90\%$ reduction in Serum IgM from baseline)
Extramedullary Disease by Physical Examination	
 
Spleen and/or Lymph nodes which were assessed as Enlarged at baseline are assessed as Normal/Not Enlarged or
 
No EMD is present at baseline and post-baseline
 

Radiology Overall Response	
 
Any but PD
 

New Symptomatic Disease	Absent
Minor Response	No new signs of active disease or progression
Serum IgM	MR ( $\geq 25\%$ and $< 50\%$ reduction in Serum IgM from baseline)
Extramedullary Disease by Physical Examination	
 
Spleen and/or Lymph nodes which were assessed as 'Enlarged at baseline' are assessed as 'Normal/Not Enlarged' or 'Enlarged – Reduction from baseline' or
 
No EMD is present at baseline and post-baseline
 

Radiology Overall Response	
 
Any but PD
 

New Symptomatic Disease	Absent
Stable Disease	Not meeting the criteria for CR, VGPR, PR, MR, PD, NE or NED
Progressive Disease (PD)	Any of the categories meet the criteria for progression
Serum IgM	
 
PD unconfirmed, or
 
PD confirmed if serum IgM is the only indicator of PD (<math>\geq 25\%</math> in serum IgM from nadir)
 
Absolute increase of <math>> 5</math> g/L is required when increase of IgM is the only applicable criterion
 

Extramedullary Disease by Physical Examination	
Either spleen or lymph nodes are assessed as 'Enlarged New/recurrent' or 'Enlarged- Unequivocal Progression'
 
Progression due to lymph node/spleen enlargement by PE only should be unequivocal, and cannot drive progressive disease unless supported by other data (eg, IgM meets the criteria for PD as defined above)

Radiology Overall Response	PD
Bone Marrow	Positive (New or recurrent involvement in bone marrow associated with WM)
New Symptomatic Disease	Yes
Not evaluable	NE require AT LEAST ONE of the following, and no evidence of PD
Serum IgM	
Not available/evaluable or
 
All available IgM values are confounded by plasmapheresis

Extramedullary Disease by Physical Examination	Spleen and/or Lymph nodes were assessed as Enlarged at baseline and follow-up assessments are not performed
Radiology Overall Assessment	NE
Cryoglobulinemia	If cryoglobulinemia is present, the overall tumor response can be NE based on the independent reviewer's oncological judgment.
New lesions	None

Response and Sub-categories for assessment	Overall Timepoint Assessment
No Evidence of Disease (NED)	All criteria have to be met
Serum IgM	Serum IgM or Serum M-Protein SPED was assessed as Normal at baseline and CR at Post-baseline
Extramedullary Disease by Physical Examination	No EMD at baseline and Post-baseline
Radiology Overall Assessment	NED
Bone Marrow	Negative at baseline and post-baseline
New Symptomatic Disease	None
Abbreviations: CR=complete response; EMD=extramedullary disease; IgM=immunoglobulin M; MR=minor response; NA=not applicable; NE=not evaluable; NED=no evidence of disease; PD=progressive disease; PE=physical examination; PR=partial response; SPED=serum protein electrophoresis; VGPR=very good partial response; WM=Waldenström's macroglobulinemia.	

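### In the WM/LPL response table, shrinking but still enlarged disease on examination is graded minor response at a 25-49% IgM fall but stable disease at 50-89%, so the grade drops as IgM improves

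*Combined protocol and SAP*

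**What the plan says.** All of the following is in the IWWM table of Section 10.9.3.3 (Appendix 9) unless stated.

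- **PR.** The row is conjunctive: "All criteria have to met". IgM must have fallen by at least 50% and less than 90%. On examination the requirement is "Spleen and/or Lymph nodes which were assessed as Enlarged at baseline are assessed as Normal/Not Enlarged or", with the alternative that no extramedullary disease is present at baseline or afterwards. Radiology may be anything except progression, and there must be no new symptomatic disease.
- **MR.** IgM must have fallen by at least 25% and less than 50%. The spleen or nodes "are assessed as 'Normal/Not Enlarged' or 'Enlarged – Reduction from baseline' or" (again) there is no extramedullary disease. Radiology is as for PR. Section 4.2.1.1 gives the same IgM band for MR, 25 to 49%.
- **VGPR.** IgM must have fallen by at least 90% or be normal. The examination item has the same wording as in PR, and radiology must be CR or PR.
- **Stable disease.** This is the residual category: "Not meeting the criteria for CR, VGPR, PR, MR, PD, NE or NED".
- **Imaging.** In Section 10.9.3.2.2, a target-lesion PR is a 1% or greater "decrease in SPD of target lesions from baseline, and no individual lesion meets the criteria for progression". The spleen likewise needs only a 1% decrease in excess length.
- **Endpoints.** Section 3 defines WM/LPL objective response as CR, VGPR or PR (secondary). An exploratory version adds MR. Section 9.4.2 starts DOR at the first documented objective response.

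**The concern.** A response scale should not move a participant to a worse category because one component improves while the others stay the same. Here the category "Enlarged – Reduction from baseline" is available in the MR row and absent from the PR row, while MR has an upper IgM limit. A participant whose nodes are shrinking but still enlarged therefore has no response category once the IgM fall reaches 50%.

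The examination item is also out of line with the rest of the PR row. PR is compatible with stable disease on imaging, and imaging PR needs only a 1% decrease, yet residual enlargement on examination blocks PR whatever the scan shows. For progression, the same table treats examination findings as too weak to decide alone and asks for supporting data.

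At stake are the secondary WM/LPL ORR, the exploratory ORR including MR, and the start date of DOR. A site that follows the table literally and a site that corrects it by judgement would grade the same record differently.

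**Working it through.** The documents state no figure for this point, so the check is logical: apply the rows to each combination of IgM fall, examination finding and radiology result.

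**Conditions.** Spleen or nodes enlarged on baseline examination; IgM still above normal; no progression; nothing missing; no new symptoms. CR is not in play.

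| IgM fall | Examination normal | Reduced but still enlarged | Enlarged, unchanged |
|---|---|---|---|
| 20% | SD | SD | SD |
| 25, 30, 49% | MR | MR | SD |
| 50, 60, 75, 89% | PR | **SD** | SD |
| 90, 95% | VGPR (SD if radiology is only SD) | **SD** | SD |

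The middle column is the same whether radiology is CR, PR or SD.

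**Why 50-89% with a reduction is SD.** PR fails on the examination item. MR fails because the IgM fall is not below 50%. VGPR fails because the fall is below 90%; if IgM has become normal, VGPR fails on its own examination item instead. Nothing else applies, so the residual category does.

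**Example.** Two participants have the same reduced but still enlarged nodes and no progression on CT. With an IgM fall of 30% the grade is MR; with a fall of 70% it is SD.

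**Effect of amending the PR examination item alone.** The middle column becomes MR at 25-49%, PR at 50-89% and still SD at 90% or more. VGPR has the same examination item and PR stops below 90%, so the drop moves from the 50% boundary to the 90% boundary.

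**Size for ORR.** One reclassified participant changes ORR by 1/n. Section 9.6.2 specifies exact 95% Clopper-Pearson intervals. The same calculation returns the interval that Section 2.2.2.3 states for 9 of 23 responders (19.7% to 61.5%). The n and the response counts below are assumptions, because the plan gives no number of WM/LPL participants:

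- n = 3: 0/3 (0 to 70.8%) becomes 1/3 (0.8 to 90.6%), a shift of 1/3 = 33 points.
- n = 6: 1/6 (0.4 to 64.1%) becomes 2/6 (4.3 to 77.7%), a shift of 1/6 = 17 points.
- n = 12: 3/12 (5.5 to 57.2%) becomes 4/12 (9.9 to 65.1%), a shift of 1/12 = 8 points.

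The last case takes n at the top of the planned enrolment of 6 to 12 across all diseases (Section 1.1).

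**The case against.** The literal reading of the table is not in dispute, and no other section overrides it: Section 8.2.1.3 sends the reader to Appendix 9. The case on the other side concerns reach and consequence, and much of it stands.

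- **Loss from ORR.** A reader might infer that every such participant drops out of ORR and that DOR never starts. The table grades single timepoints, and Section 8.2 repeats assessments every 12 weeks. If the examination later becomes normal while the other PR items hold, that timepoint is PR and DOR starts then.
- **Frequency.** A reader might infer from inclusion criterion 3, which lists bulky or symptomatic nodes and symptomatic splenomegaly, that the pattern is to be expected. That criterion needs only one of several features. Criterion 4 allows measurable disease by IgM or marrow alone, and Section 10.9.3.1 provides for participants without extramedullary disease. The number affected could be zero.
- **Which cell is wrong.** A reader might infer that PR is the correct grade and that ORR is biased downward. The table shows only that its rows are out of order. The cited IWWM publication is not among the documents, so they do not settle whether the PR item, the MR option or the IgM limits depart from it.
- **Judgement on examination.** The IWWM section gives no size at which a node on examination stops being enlarged, so some records near that line would be graded differently by different assessors in any case.
- **Importance.** The primary endpoints are safety endpoints, no hypothesis is tested, and escalation depends on DLTs. No decision rule uses WM/LPL ORR.

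None of this removes the drop in grade between a 49% and a 50% IgM fall.

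**Conclusion.** The point holds as an internal defect of the table. Under the conditions listed, a WM/LPL timepoint with reduced but still enlarged spleen or nodes is MR at a 25-49% IgM fall and SD at 50-89%. That timepoint is then excluded from both the secondary ORR and the exploratory ORR including MR, although a smaller IgM fall would have counted in the latter.

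The consequence for a participant depends on the other assessments: loss from ORR if none reaches PR or better, a later DOR start otherwise. The effect on ORR is 1/n per reclassified participant, 33 to 8 points over the assumed n of 3 to 12, and nil if nobody shows the pattern. This is worth correcting because it affects the grading of a secondary endpoint in very small groups. It does not touch the safety conclusions or the dose-finding rules.

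**What to change.** Reconcile the PR, MR and VGPR rows of Section 10.9.3.3 together, so that the categories are ordered and exhaustive:

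1. Add the reduced-but-still-enlarged option to the PR examination item, using the category that the MR row already has.
2. In the same edit, let a participant with an IgM fall of at least 90%, or normal IgM, who misses VGPR only on the examination item be graded PR rather than SD. Otherwise the drop moves to the 90% boundary.
3. Close the parallel gap shown in the working table, where an IgM fall of 90% or more with radiology of only SD also ends in SD. Wording that covers steps 2 and 3 is to define the PR IgM item as a fall of at least 50%, or normal IgM, in a participant who does not meet VGPR or CR.
4. Check the resulting rows against the cited IWWM criteria before finalising them.

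Because this changes how a secondary endpoint is graded, make it by protocol amendment before database lock (Section 9 requires an amendment for changes to secondary objectives or their methods). Apply it to all WM/LPL timepoints.

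The text change is small and needs no new category. The real cost is that earlier WM/LPL timepoints must be regraded in an open-label study with results already known. Reporting ORR under both the current and the amended table would show whether the change matters.
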